8.4.6. Pregnancy

Female participants who become pregnant after the first study intervention dose must not receive subsequent doses of the study intervention but may continue other study procedures at the discretion of the investigator.

- Details of all pregnancies in female participants will be collected after the start of study intervention and until 48 hours after the last study intervention.
- If a pregnancy is reported, the investigator will record pregnancy information on the appropriate form and submit it to the sponsor within 24 hours of learning of the female participant pregnancy.
- Any pregnancy or pregnancy complication or elective termination of a pregnancy for medical reasons will be reported as an AE or SAE.
- Abnormal pregnancy outcomes (e.g., spontaneous abortion, fetal death, stillbirth, congenital anomalies, ectopic pregnancy) are considered SAEs and will be reported as such.
- The participant will be followed to determine the outcome of the pregnancy. The investigator will collect follow-up information on the participant/pregnant female partner and the neonate, and the information will be forwarded to the sponsor. See Table 6 for reporting timeframes.

- Any poststudy pregnancy-related SAE considered reasonably related to the study intervention by the investigator will be reported to the sponsor as described in Section 8.4.4. While the investigator is not obligated to actively seek this information in former study participants, he or she may learn of an SAE through spontaneous reporting.
- Any female participant who becomes pregnant while participating in the study will discontinue study intervention or be withdrawn from the study.

8.4.7. CV and Death Events

CV Events

Not applicable.

Death Events

The Death eCRF is provided immediately after the occurrence or outcome of death is reported. Initial and follow-up reports regarding death must be completed within 1 week of when the death is reported.

8.4.8. Disease-related events and/or disease-related outcomes not qualifying as AEs or SAEs

Not applicable.

8.4.10. Participant card

Not applicable.

8.4.11. Medical device deficiencies

Medical devices are being provided for use in this study as the study intervention. To fulfill regulatory reporting obligations worldwide, the investigator is responsible for the

detection and documentation of events meeting the definitions of device deficiency that occur during the study with such devices.

The definition of a medical device deficiency can be found in Section [10.6](#).

NOTE: Deficiencies fulfilling the definition of an AE/SAE will follow the processes outlined in Section [10.6](#) of the protocol.

8.4.11.1. Time Period for Detecting Medical Device Deficiencies

- Medical device deficiencies that result in an incident will be detected, documented, and reported during all periods of the study in which the medical device is used.
- If the investigator learns of any device deficiency at any time after a participant has been discharged from the study, and such a deficiency is considered reasonably related to a medical device provided for the study, the investigator will promptly notify the sponsor.

The method of documenting medical device deficiencies is provided in Section [10.6](#).

8.4.11.2. Follow-up of Medical Device Deficiencies

- Follow-up applies to all participants, including those who discontinue study intervention.
- The investigator is responsible for ensuring that follow-up includes any supplemental investigations as indicated to elucidate the nature and/or causality of the deficiency.
- New or updated information will be recorded on the originally completed form with all changes signed and dated by the investigator.

8.4.11.3. Prompt Reporting of Device Deficiencies to the Sponsor

- Device deficiencies will be reported to the sponsor within 24 hours after the investigator determines that the event meets the protocol definition of a medical device deficiency.
- The medical device deficiency report form will be sent to the sponsor by email/facsimile equipment. If email/facsimile equipment is unavailable, then notification by telephone with a copy of data collection tool sent by overnight courier service should be utilized.
- The sponsor will be the contact for the receipt of device deficiency reports.

8.4.11.4. Regulatory Reporting Requirements for Device Deficiencies

- The investigator will promptly report all device deficiencies occurring with any medical device provided for use in the study in order for the sponsor to fulfill the legal responsibility to notify appropriate regulatory authorities and other entities about certain safety information relating to medical devices being used in clinical studies.

- The investigator, or responsible person according to local requirements (e.g., the head of the medical institution), will comply with the applicable local regulatory requirements relating to the reporting of device deficiencies to the IRB/IEC.

8.5. Pharmacokinetics

Whole blood samples of approximately 4.5 mL will be collected for measurement of plasma concentrations of salbutamol as specified in the SoA (Section 1.3).

CCI

Instructions for the collection and handling of plasma samples will be provided by the sponsor. The actual date and time (24-hour clock time) of each sample will be recorded.

Details of PK blood sampling collection, processing, storage, and shipping procedures are provided in the Lab Manual prepared by GSK.

8.6. Pharmacodynamics

The following PD parameters will be evaluated and compared: serum potassium weighted means and minimum serum potassium.

Blood samples of approximately 3.5 mL will be collected for measurement of potassium concentrations in serum as specified in the SoA (Section 1.3).

Serum potassium concentrations will be assessed by the CCI

8.7. Genetics

Not applicable.

8.8. Biomarkers

Not applicable.

8.9. Immunogenicity assessments

Not applicable.

8.10. Health economics or medical resource utilization and health economics

Neither health economics or medical resource utilization and health economics parameters are evaluated in this study.

9. STATISTICAL CONSIDERATIONS

The statistical analysis plan will include a more technical and detailed description of the statistical analyses described in this section. This section is a summary of the planned statistical analyses of the most important endpoints including primary and key secondary endpoints.

Any deviation from the statistical analysis plan will be reported in the section “Changes in Planned Analysis” in the CSR.

9.1. Statistical hypotheses

This study is designed to estimate the relative bioavailability of salbutamol HFA-152a (test) and Salbutamol HFA-134a (reference) in following cohorts:

Cohort 1: Salbutamol HFA-152a 200 µg, Salbutamol HFA-134a 200 µg.

Cohort 2: Salbutamol HFA-152a 800 µg, Salbutamol HFA-134a 800 µg.

In each cohort, for each PK parameters endpoints (AUC(0-30min.), AUC(0-∞), Cmax and AUC(0-last)), point estimates and corresponding 90% CIs will be constructed for GMR(T/R).

90% Confidence Interval of GMR (T/R): The GMR is calculated by taking the ratio of the geometric means of the salbutamol HFA-152a (T) to the salbutamol HFA-134a (R). The 90% confidence interval of this GMR is a range that provides a measure of the uncertainty in this ratio.

An additional assessment will be performed by comparing the 90% CIs for the GMR(T/R) in AUC(0-30min), AUC(0-∞), Cmax and AUC(0-last) PK parameters to the bioequivalence acceptance range (refer to Section 10.8, [Table 12](#)).

9.1.1. Multiplicity Adjustment

No multiplicity adjustment will be performed for the primary or secondary endpoints.

9.2. Analysis sets

Analysis Set	Definition/Criteria	Analyses Evaluated
Screened	
 • All participants who were screened for eligibility. 	All Screened, Reason for Screen Failures
Enrolled	
 • All participants who screen passed and entered in the study (who were randomized). • Note screening failures (who never passed screening even if rescreened) and participants screened but never enrolled into the study (met eligibility but not needed) are excluded from the enrolled analysis set as they did not enter the study. 	Study Population
FAS	
 • All randomized participants who received at least a single dose period of study intervention • Data will be reported according to the randomized study intervention. 	Exploratory PD objective
Safety	
 • All participants who received at least one puff/actuation of study intervention. 	Estimand for secondary safety objective
PK	
 • All participants in the FAS who had at least 1 non-missing PK assessment (NQ values will be considered as non-missing values). • Data will be reported according to the actual study intervention. 	Estimand for primary and secondary objective of PK parameters

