3.1. Primary Estimands

Cohort 1:

Test: Salbutamol HFA-152a MDI 200 µg

Reference: Salbutamol HFA-134a MDI 200 µg

The primary clinical question of interest for Cohort 1 is-

What is the GMR for Cohort 1 in primary PK parameters (AUC(0-30min), AUC(0-∞) and Cmax) of salbutamol HFA-152a and salbutamol HFA-134a in healthy participants after administration of single dose of 200 μg?

The primary estimand for Cohort 1 is described by the following attributes:

- The population is healthy male or female participants aged 18 to 55 years.
- The primary PK parameters endpoints are AUC(0-30min), AUC(0-∞) and Cmax.
- Treatment condition is administration of salbutamol as a single 200 μg dose, given as 2 actuations each separated by a 20-second interval, each delivering 100 μg of salbutamol (as salbutamol sulfate) as the ex-valve dose for the HFA-152a MDI or HFA-134a MDI.
- The ICEs and estimand strategies are as follows:
 - Study treatment discontinuation due to any reason (hypothetical strategy).
 - Occurrence of emesis or coughing on dosing (hypothetical strategy).
 - Dosing error: Considered less than or more than prescribed dose (hypothetical strategy).
 - Use of prohibited or rescue medication which impacts to PK parameters (hypothetical strategy).

For all ICEs, interest lies in evaluating the primary PK parameters and comparisons of the ratio of 2 formulations for each primary PK parameters in a hypothetical scenario in which the participant had not experienced an intercurrent event. This is to minimize potential confounding of ICEs on individual PK parameters across treatment periods.

- The population-level summary to be estimated is:

Ratio of adjusted GM (for logarithmic transformed values) of 2 formulations with 90% CI for each primary PK endpoint.

Cohort 2:

Test: Salbutamol HFA-152a MDI 800 μg

Reference: Salbutamol HFA-134a MDI 800 μg

The primary clinical question of interest for Cohort 2 is –

What is the GMR for Cohort 2 in primary PK parameters (AUC(0-30min), AUC(0-∞) and Cmax) of salbutamol HFA-152a and salbutamol HFA-134a in healthy participants after administration of single dose of 800 μg?

The estimand for Cohort 2 has the same estimand attributes as Cohort 1 (population, PK endpoints, population-level summary measure, ICE strategy), except for the attribute for the treatment condition:

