9.3.2. Tertiary/exploratory endpoint(s) analysis

9.3.2.1. Pharmacodynamic analysis

For each cohort, the following PD parameters will be evaluated and compared between Salbutamol HFA-152a MDI (test) and Salbutamol HFA-134a MDI (reference): minimum serum potassium, MHR and maximum QTcF interval.

Following log_e-transformation, minimum serum potassium, MHR and maximum QTcF interval will be analyzed using mixed effect model approach with fixed effect for period, treatment group and participants as random effects. The point estimates and their associated 90% CI will then be back-transformed to provide point estimates and 90% CI for the ratios (GMR) of HFA-152a MDI (test)/HFA-134a MDI (reference).

The exploratory PD parameters data will be summarized using descriptive statistics (N, n, AM, GM, SD, SD in log scale CV %, median, minimum, and maximum), and will be summarized in tabular and/or graphical form.

CCI

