### 3. ANALYSIS SETS

Analysis Set	Definition / Criteria	Analyses Evaluated
Screened	
 
• All participants who were screened for eligibility.
 
	
 
• All Screened Reason for Screen Failures
 

Enrolled	
 
• All participants who screen passed and entered in the study (who were randomized or received treatment or underwent a post-screening study procedure)
 
• Note screening failures (who never passed screening even if rescreened) and participants screened but never enrolled into the study (met eligibility but not needed) are excluded from the enrolled analysis set as they did not enter the study
 
	
 
• Study Population
 

FAS	
 
• All randomized participants who received at least a single dose period of study intervention
 
• Data will be reported according to the randomized study intervention.
 
• Single dose = 2 puffs/actuations for Cohort 1
 
• Single dose = 8 puffs/actuations for Cohort 2
 
	
 
• Study Population
 
• Exploratory PD objective
 

Safety	
 
• All participants who received at least one puff/actuation of study intervention.
 
• Data will be reported according to the actual study intervention.
 
	
 
• Estimand for secondary safety objective
 

Pharmacokinetic (PK)	
 
• All participants in the FAS who had at least 1 non-missing PK assessment (NQ values will be considered as non-missing values).
 
• Data will be reported according to the actual study intervention.
 
	
 
• Estimand for primary and secondary objective of PK parameters
 

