#### 4.4. Exploratory Endpoint(s) Analyses

The exploratory pharmacodynamics (PD) endpoints are -

- Minimum serum potassium
- MHR
- Maximum QTc interval

The exploratory pharmacodynamics (PD) endpoints will be analyzed for Cohort 1 and Cohort 2 using FAS. All PD parameters will be summarized by study treatment.

Statistical model for the analysis of exploratory PD endpoints in each cohort

Following loge-transformation, minimum serum potassium, MHR and maximum QTcF interval will be analyzed using mixed effect model approach with fixed effect for period, treatment group. The point estimates and their associated 90% CI will then be back-transformed to provide point estimates and 90% CI for the ratios (GMR) of HFA-152a MDI (test)/HFA-134a MDI (reference).

For the untransformed data of pharmacodynamics (PD) parameters (minimum serum potassium, MHR (Maximum HR, maximum QTc interval)), descriptive statistics (N, n, AM, 95% CI of AM, SD) median, minimum and maximum) will be computed for FAS.

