Descriptive statistics (n, mean, standard deviation (SD), median, minimum value (min), and maximum value (max)) will be presented for quantitative measurements of absolute value for continuous laboratory parameters (clinical chemistry and hematology) including serum potassium and glucose at baseline and each assessed visit as per SOA of protocol in on-treatment period for Safety analysis set. Counts and percentages will be produced for qualitative measurements measure laboratory parameters for on-treatment period for Safety analysis set.

As per protocol SOA Section 1.3, safety laboratory parameters data are not collected for follow up visit, therefore on-treatment period will be same as overall period.

Summary of liver monitoring/stopping event will be summarized by counts and percentages. Refer to protocol Appendix 5, Section 10.5 Liver safety for more description of liver events.

Participants listing of all clinical laboratory data will be produced for each treatment and period in Safety analysis set.

If a laboratory value which is expected to have a numeric value for summary purposes, has a non-detectable level reported in the database, where the numeric value is missing, but typically a character value starting with ‘<=’ or ‘=>’ (or indicated as less than x or greater than x in the comment field) is present, the number of significant digits in the observed values will be used to determine how much to add or subtract in order to impute the corresponding numeric value.

- Example 1: 2 significant digits = ‘<= x’ becomes  $x - 0.01$
- Example 2: 1 significant digit = ‘=> x’ becomes  $x + 0.1$
- Example 3: 0 significant digits = ‘<=x’ becomes  $x - 1$

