#### 4.5.3.3. ECG

The arithmetic mean of the three recorded 12-lead ECGs measurements will be presented in all data summaries of 12-lead ECGs measurements at predose and single measurement of post dose for days 1, 4, 7 and 10 and discharge. ECG measurements will be recorded, including heart rate (HR), PR interval, QRS duration, QT interval, and RR interval. QT intervals will be based on Fridericia's formula and reported as per captured in eCRF:

Descriptive statistics (n, mean, standard deviation (SD), median, minimum value (min), and maximum value (max)) will be presented at baseline, and absolute and change from baseline for HR, QTc and other ECG parameters at each assessed visit for on-treatment period for Safety analysis set.

As per protocol SOA Section 1.3, safety ECG data are not collected for follow up visit, therefore on-treatment period will be same as overall period.

Participants listings will be provided for all 12 lead ECGs values and findings including abnormal ECGs for each treatment sequence and period in Safety analysis set.

[figure not shown]

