#### 6.1.1. Participant Disposition

Participant disposition will be tabulated by each treatment sequence, each period (with primary reason for withdrawal including washout period) for all participants combined with the counts and percentages of participants who complete the study, prematurely withdraw, and the reason for study withdrawal for Enrolled participants. Participants disposition will also be summarized for FAS if the difference finds between Enrolled and FAS participants.

Summary of treatment status and reasons for discontinuation of study treatment will be produced for study treatment, with the number of participants who completed study

treatment, or prematurely discontinued treatment, and the primary reasons for treatment discontinuation tabulated for the FAS.

Participant listing of the reasons for study withdrawal will be provided for each treatment sequence and period in enrolled participants.

Summary of screen failure and its reason as per eCRF will be provided for overall (Total) screened participants.

Table will be generated for summarizing the number of participants in each analysis set for all participants who provided informed consent. Listing of participants excluded from any analysis set will also be produced for Enrolled participants. Listing of planned and actual treatment will also be generated.

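### Exploratory PD is labelled by randomized product while PK and (in the SAP) safety follow the product given, so a wrong-product dose would be counted inconsistently and would slightly dilute the PD ratio

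*Protocol*

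**What the plan says.** Protocol 9.2 and SAP 3 both define the FAS with the rule "Data will be reported according to the randomized study intervention", and both assign the exploratory PD objective to it. SAP 4.4 confirms this: "The exploratory pharmacodynamics (PD) endpoints will be analyzed for Cohort 1 and Cohort 2 using FAS". The PD model in Protocol 9.3.2.1 is a treatment comparison: "minimum serum potassium, MHR and maximum QTcF interval will be analyzed using mixed effect model approach with fixed effect for period, treatment group", with results back-transformed to a test/reference ratio and 90% CI.

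The PK set is a subset of the FAS but has the opposite rule in both documents: "Data will be reported according to the actual study intervention". SAP 3 gives that same rule for the Safety set. The Safety row in Protocol 9.2 has no labelling rule.

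The PD variables are also safety data. SAP 4.5.3.1 summarizes laboratory values on the Safety set "including serum potassium and glucose at baseline and each assessed visit", and SAP 4.5.3.3 summarizes "absolute and change from baseline for HR, QTc and other ECG parameters at each assessed visit" on the same set.

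The dosing-error intercurrent event is defined by amount: "Dosing error: Considered less than or more than prescribed dose (hypothetical strategy" (Protocol 3.1, repeated in SAP 1.1). It does not name a dose of the wrong product. Estimands are set out for PK and safety, not for PD. SAP 6.1.1 adds: "Listing of planned and actual treatment will also be generated".

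**The concern.** The PD objective is to characterize and compare what each product does. If a participant inhales from the wrong device in one period, the potassium, heart rate and QTc of that period reflect the product inhaled. Under the stated rules they appear under that product in the safety summaries and under the other product in the PD ratio. The PK of the same period would also carry the opposite label from its PD.

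The mislabelling has a direction. It mixes the two products in the PD contrast and draws the expected ratio towards 1. In a study meant to show that two products are comparable, labelling by randomization is therefore not the cautious default that it is in a superiority trial. Protocol 2.3.1 names the possibility that the new propellant delivers a higher effective dose, with effects on potassium and QTc. The PD ratio is the modelled comparison of those effects, because the safety summaries are descriptive.

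**Working it through.** **The plan's own figure.** The documents give no figure for PD labelling. The nearest is the PK half-width of 16.44% (Protocol 9.5, SAP 5) for n = 28 and a within-subject CV of 50%. With sw = sqrt(ln(1 + 0.5²)) = 0.4724 and 26 degrees of freedom, exp(t(0.95; 26) × 0.4724/√28) - 1 = 16.447%, which agrees apart from rounding. The standard error sw/√n corresponds to two test and two reference doses per participant, the structure used below. The figure says nothing about PD precision, and the visible text gives no PD variability.

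**Inputs.**
- Sequences TRRT and RTTR, 15 participants each, 30 per cohort (Protocol 4.1). This gives 60 test and 60 reference periods per cohort.
- One PD value per participant per period (assumption).
- True PD ratio and number of wrong-product doses: not given. Assumed ratios are 0.90, 1.00, 1.10 and 1.25. Assumed mix-ups run from one dose to three participants on the wrong sequence.

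**Formula.** Every period has 15 test and 15 reference doses, and every participant has two of each. Treatment is therefore orthogonal to period and to participant, and the estimated log ratio is the mean of the 60 test-labelled log values minus the mean of the 60 reference-labelled ones. Let δ be the true log ratio, a the number of test-labelled periods that received reference, and b the number of reference-labelled periods that received test. Then

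E(estimate) = δ(60 - a)/60 - δb/60 = δ(1 - k/60), with k = a + b.

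A least-squares fit of period and randomized treatment gave the same factors with and without participant effects. The SAP's removal of the participant random effect from the PD model therefore does not alter them.

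**Results (estimated ratio = true ratio raised to the factor).**

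| Mix-up in a cohort of 30 | k | Factor | True 0.90 | True 1.00 | True 1.10 | True 1.25 |
|---|---|---|---|---|---|---|
| One wrong-product dose | 1 | 59/60 = 0.983 | 0.902 | 1.000 | 1.098 | 1.245 |
| One T/R swap within a participant | 2 | 58/60 = 0.967 | 0.903 | 1.000 | 1.097 | 1.241 |
| One participant, whole wrong sequence | 4 | 56/60 = 0.933 | 0.906 | 1.000 | 1.093 | 1.232 |
| Two such participants | 8 | 52/60 = 0.867 | 0.913 | 1.000 | 1.086 | 1.213 |
| Three such participants | 12 | 48/60 = 0.800 | 0.919 | 1.000 | 1.079 | 1.195 |

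With 28 participants the divisor is 56: one dose gives 55/56 = 0.982 and one whole wrong sequence gives 52/56 = 0.929. Labelled by the product given, the factor is 1.000 in every row.

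**The case against.** The strongest reply is that this is a convention, stated openly and repeated in both documents: full analysis set by randomization, PK and safety by treatment received. Participants are confined at a single centre and dosed directly by site staff under supervision (Protocol 6.5), so wrong-product doses should be rare. PD is exploratory, and the visible text gives it no acceptance range; the comparison with a bioequivalence range in Protocol 9.1 is for PK parameters. This stands, and it is why the point is minor. It does not remove the inconsistency, because no visible rule says how a wrong-product period enters the PD ratio.

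Three stronger inferences are not supported.

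- A reader might conclude that PD and PK from an affected period cannot be reconciled. They can: the SAP lists planned and actual treatment (6.1.1), dose administration by treatment and period (4.5.1), and important deviations by treatment and period (6.1.3).
- A reader might take the planned/actual listing as a sign that mix-ups are expected. It makes provision for them and says nothing about their rate.
- A reader might argue that part-dosed, emesis or coughing periods must leave the PD ratio as they leave PK. That is a separate estimand choice. Such periods can move the ratio either way, so the argument about direction does not cover them. PK data are set to missing only where the event affects the concentrations (Protocol 9.3.1.3, SAP 4.2.2), so there is no automatic exclusion for PD to copy.

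**Conclusion.** The labelling mismatch is real and the direction of its effect is correct, but the consequence is small. One wrong-product dose takes 1.7% off the PD log ratio and one participant on the whole wrong sequence takes off 6.7%. On the ratio scale an assumed 1.10 becomes 1.098 or 1.093. The 6.7% should not be read as a change in the ratio itself.

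The conclusion rests on these conditions:
- A wrong-product dose must occur, and the true ratio must differ from 1. The pull towards 1 is in expectation, not a certainty in one data set.
- There must be one PD value per participant per period. The SAP version history says each participant has a single observation for the study, which does not fit a four-period comparison. That needs its own clarification.
- Labelling of safety by actual product rests on SAP 3 alone, since the Protocol's Safety row gives no rule.

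The primary PK analysis already follows the product given and is not affected. The main gain from a change is coherence: the same reading should not count for both products in one report.

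**What to change.** Keep the FAS as the set of participants for PD. In Protocol 9.2, SAP 3 and SAP 4.4, state that PD data are labelled and modelled by the actual study intervention in each period. In Protocol 9.2, add to the Safety row the line on actual intervention that SAP 3 already has.

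The cost is a few sentences. The actual-treatment variable is already needed for PK and safety, and relabelling loses no PD period. The rule should be fixed before any mix-up is known: the study is open-label with an interim analysis after Cohort 1, and choosing the label afterwards would be post hoc.

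Excluding PD periods for part-dosing, emesis or coughing is not part of this change. If wanted, it should be added only as a sensitivity analysis.
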